7.2.1.1. Handling of Dropouts or Missing Data

Subjects who prematurely discontinue from the study will be included up to the time of discontinuation.

7.2.1.2. Subgroup Analysis

There is no planned subgroup analysis.

7.2.1.3. Multicenter Studies

Not applicable.

7.2.1.4. Hypothesis Testing and Significance Level

As this study is an exploratory study, no formal hypothesis testing is being conducted. The study results will be summarized using descriptive statistics.

7.2.1.5. Sensitivity Analyses

As a part of sensitivity analysis, the primary analysis in Section 7.2.1 will also be performed on the PP Set.

Sensitivity analysis will only be performed when the number of participants in the PP Set is at least 3.

7.2.2. Secondary Analyses

Secondary analyses will be performed using the FA Set. The secondary endpoints include:

- Change from pre-dose baseline in mean daily copper balance during ALXN1840 accumulation and steady-state periods for each dose
- Mean daily copper quantified in food, drink, feces, and urine, and mean plasma total copper, and mean LBC, during ALXN1840 accumulation and steady-state periods for each dose
- Mean daily molybdenum quantified in food, drink, feces, and urine, and mean plasma total molybdenum, during ALXN1840 steady-state period for each dose

- Mean daily molybdenum balance as demonstrated through measurement of molybdenum intake (in food, drink and ALXN1840), and molybdenum output (feces and urine), during ALXN1840 steady-state period for each dose
- Accumulation of molybdenum as determined by molybdenum balance
- PK parameters for plasma total and PUF-molybdenum

The secondary continuous endpoints will be analyzed using the same methods described for the primary analysis. Molybdenum balance will include the additional molybdenum intake from ALXN1840. The nominal amount of molybdenum contained in ALXN1840 will be used and is estimated as 3.33 mg in each 15 mg tablet per the following calculation: $95.96 \text{ g/mol (molecular weight of molybdenum)} / 432.54 \text{ g/mol (molecular weight of bis-choline tetrathiomolybdate)} * 15 \text{ mg/tablet} = 3.33 \text{ mg molybdenum}$. The periods of interest described in Section 7.2.1 will be utilized as appropriate. The daily molybdenum balance for each subject will be plotted as will the mean daily molybdenum balance.

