We hypothesize that repeated doses of ALXN1840 may drive a net negative copper balance in participants with WD by increasing fecal excretion of copper. In this study, copper balance will be calculated as the difference between measured copper input in food and drink and measured copper output in urine and feces. This method is classically considered the most objective measure of decoppering ability with a decoppering agent able to drive a net negative copper balance (Hill, 1986; Strickland, 1971; Walshe, 1973). The purpose of this study is to provide additional descriptive characterization of the effect of ALXN1840 on copper balance in participants with WD. Further data obtained may help support characterization of a “decoppering” versus “maintenance” dose of ALXN1840, where a decoppering dose would be a dose sufficient to drive a net negative copper balance and maintenance would support a more neutral copper balance.

The secondary aim of the study is to characterize the steady-state ADME (mass balance) of total molybdenum as a surrogate measure of ALXN1840 disposition in participants with WD. To confirm that steady state is adequately characterized by the plasma PK, a molybdenum mass balance assessment will be performed on Day 25 through Day 28 for the 15 mg/day dose and Day 36 through Day 39 for the 30 mg/day dose: if steady state is achieved, molybdenum(out) will equal molybdenum(in).

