8.1. Efficacy Assessments

8.1.1. Copper and Molybdenum Balance Measurements

Copper and molybdenum balance measurements will be made on all intake (ie, investigational agent, food and fluids) and all output (urine and feces) from participants as indicated in the SoA. The copper and molybdenum concentration of each sample will be determined by inductively coupled plasma mass spectrometry (ICP-MS). Copper and molybdenum content of all intake and output will be calculated based on the volume or weight of intake and output and the concentration of representative samples.

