4.1. Changes From Analyses Specified in the Protocol

Not applicable. There are no changes from the protocol.

4.2. Changes From Analyses Specified in the Previous Version of the Statistical Analysis Plan

The following updates have been made to the SAP version 1.0 approved 11 Jun 2021:

- Added analyses for WD history. (Section [7.1.3.3](#))
- Added analyses for prior medications used to treat WD. (Section [7.1.4](#))
- Added language to clarify that sensitivity analysis will only be performed when the number of participants in the Per Protocol Set is at least 3. (Section [7.2.1.5](#))
- Added analyses for Cu and Mo input, output, and input to output sources on a percentage basis. (Section [7.2.3](#)).

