For ALXN1840, equivalent molybdenum dose will be used to calculate total molybdenum CL/F and V_d/F values as described in Section 7.2.2. For ALXN1840 30 mg equivalent molybdenum dose is 6.66 mg.

Additional plasma PK parameters may be calculated if deemed appropriate.

For the PK analysis, values below the limit of quantification (BLQ) prior to the first measurable concentration will be set to zero whereas the rest of all other BLQ values will be treated as missing.

Pharmacokinetic parameters derived from plasma concentrations of total molybdenum and PUF molybdenum will be presented in data listings and summarized by analyte, treatment (dose), and day using the following descriptive statistics: number of participants, arithmetic mean, SD, arithmetic CV, GM, GMCV, 95% CI, median, minimum, and maximum. Geometric mean and geometric CV will be presented for C_{\max} and AUCs only. When calculating the geometric mean, values of 0 will be discarded.

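### Molybdenum intake from tablets is entered at a calculated nominal content, so a batch-mean deviation from nominal passes directly into the secondary molybdenum balance; an assayed content, or a sensitivity range, is a cheap improvement

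*SAP*

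**What the plan says.** Protocol 8.1.1 says: "Copper and molybdenum balance measurements will be made on all intake (ie, investigational agent, food and fluids". It names ICP-MS as the assay for each sample and derives content from the amount taken in or put out and the concentration of representative samples. The molybdenum balance endpoint (Protocol 3, SAP 5.1.2) likewise describes intake from food, drink and ALXN1840 as something obtained by measurement.

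SAP 7.2.2 takes a different route for the drug: "The nominal amount of molybdenum contained in ALXN1840 will be used and is estimated as 3.33 mg in each 15 mg tablet". The value is a mass fraction calculated from molecular weights. SAP 7.4.3 carries it into the clearance and volume calculations: "For ALXN1840 30 mg equivalent molybdenum dose is 6.66 mg". SAP 4.1 states: "There are no changes from the protocol".

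The balance is used as a test against zero. Protocol 2.1 puts it as "if steady state is achieved, molybdenum(out) will equal molybdenum(in". Protocol 2.2 presents the comparison as a way to detect accumulation in the liver or other tissues that plasma PK could miss, and Protocol 4.2 defines steady state by a neutral molybdenum balance without giving a numerical margin.

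**The concern.** Food, drink, urine and feces enter the balance through assayed samples. The tablet term enters as a theoretical constant. If the batch mean is not at nominal, the difference is not noise: it has the same sign and size for everyone dosed from that batch, so averaging over about 10 participants does not reduce it.

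At stake are the secondary endpoints on molybdenum balance and accumulation. A batch below nominal overstates intake and gives a positive balance, which reads as retention. If the same mean content applies in both dose periods, the false balance doubles when the dose doubles, as dose-dependent retention would. A batch above nominal can hide real retention. Nothing planned would show this, because the only sensitivity analysis (SAP 7.2.1.5) repeats the primary copper analysis on the Per Protocol Set.

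**Working it through.** **1. The plan's own figure.** Inputs from SAP 7.2.2: 95.96 g/mol for molybdenum, 432.54 g/mol for bis-choline tetrathiomolybdate, 15 mg per tablet.

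- One tablet: 95.96 / 432.54 x 15 = 3.328 mg, which rounds to 3.33 mg.
- Two tablets: 2 x 3.328 = 6.656 mg, which rounds to 6.66 mg.

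Both figures reproduce, and the rounding error is 0.07%. As a cross-check, Protocol Table 6 gives 7.8 mg of tetrathiomolybdic acid per tablet. With assumed atomic weights of 32.06 for sulfur and 1.008 for hydrogen, its molecular weight is 95.96 + 4 x 32.06 + 2 x 1.008 = 226.22, so the tablet holds 7.8 x 95.96 / 226.22 = 3.31 mg of molybdenum. That is within 0.6% of 3.328 mg. The issue is nominal versus assayed content, not a calculation error.

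**2. The effect of a content deviation.** Let F be measured intake from food and drink, n the tablets per day, 3.33 x (1 + d) mg the true mean content per tablet, and R the true daily retention.

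- True output: F + n x 3.33 x (1 + d) - R
- Reported balance: F + n x 3.33 - output = R - d x n x 3.33

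The error is -d x 3.33 mg/day at 15 mg (n = 1) and -d x 6.66 mg/day at 30 mg (n = 2), whatever R is. The 2:1 ratio needs the same d in both periods.

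**3. Size.** The documents give no assay value or content tolerance, so d is an assumption.

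| Assumed deviation (absolute) | 15 mg/day | 30 mg/day |
|---|---|---|
| 1% | 0.03 mg/day | 0.07 mg/day |
| 2% | 0.07 mg/day | 0.13 mg/day |
| 3% | 0.10 mg/day | 0.20 mg/day |
| 5% | 0.17 mg/day | 0.33 mg/day |

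Tablets under nominal give a false positive balance; tablets over nominal give a false negative one.

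**4. Random tablet-to-tablet variation.** Each steady-state window has 4 days. With an assumed coefficient of variation of 5%:

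- One participant at 15 mg: 3.33 x 0.05 / sqrt(4) = 0.083 mg/day
- One participant at 30 mg: 3.33 x 0.05 x sqrt(2) / sqrt(4) = 0.118 mg/day
- Mean of 10 participants: dividing each by sqrt(10) gives 0.026 and 0.037 mg/day

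This part shrinks with averaging; the shared batch part does not.

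**5. Clearance.** CL/F is dose divided by AUC, so the nominal dose gives the true value divided by (1 + d). For d = 5% the ratio is 1 / 1.05 = 0.952, a shift of about the same percentage as d. Vd/F scales with dose in the same way.

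**The case against.** The strongest reply is that the SAP fills a gap and does not break a promise. The protocol's collection subsections (8.1.1.1 to 8.1.1.3) cover meals, fluids, urine and feces, and no tablet sampling is described anywhere. SAP 5.1.1.1 lists study drug among the intake for copper too, yet SAP 7.2.1 defines copper input from food and fluids only, which suggests a generic list of sources. Protocol 9.4 leaves statistical detail to the SAP, and the SAP states its calculation openly. This stands to a large extent. A reader might infer that the protocol commits the sponsor to assaying tablets; the text does not go that far. What remains is that the wording of 8.1.1 and of the endpoint does not match a calculated constant.

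Other parts of the defence also stand:

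- A reader might infer that the drug is the only unmeasured term. In fact each participant's food intake is also inferred, from batch samples and the fraction eaten.
- Steady state does not rest on the balance alone. Trough plots (SAP 7.4.1), accumulation ratios (SAP 7.4.3) and stepwise trend testing (SAP 7.4.5) do not use the nominal molybdenum content.
- A content error is constant within a dose, so with one batch it cancels when Days 25 through 28 are compared with Days 1 through 8. However, a slow tissue sink could look equally constant, and the stated test compares the level with zero.
- The study is exploratory and descriptive. Protocol 4.2 already warns that small variations in molybdenum balance may not reflect ALXN1840.

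It can also be said that the roughly 30% of a single dose found in rat liver at Day 7 (Protocol 2.2) is far larger than a 2% to 5% content error. That figure is a fraction of one dose in an animal model, not a daily balance on repeated dosing, so it does not settle what imbalance would matter here.

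**Conclusion.** The point holds as a cheap improvement to a secondary analysis. A batch-mean deviation d adds -d x 3.33 mg/day at 15 mg and -d x 6.66 mg/day at 30 mg to the reported molybdenum balance. Over an assumed 2% to 5%, that is 0.07 to 0.17 and 0.13 to 0.33 mg/day in absolute size. The algebra needs no assumption about retention; the size rests wholly on the assumed d.

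Three stronger readings are not supported. A reader might infer that the tablets are off label, but no document shows this, and the bias is potential and of unknown size. A reader might infer that every deviation distorts the balance in proportion to dose. Only the systematic part survives averaging, and the 2:1 pattern needs equal mean content in both periods, while the documents do not say that one batch is used throughout. A reader might also extend the concern to the primary endpoint, but copper input excludes the tablets. Using the nominal dose for CL/F and Vd/F is not in itself a fault; it carries the same caveat.

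**What to change.** In SAP 7.2.2, compute tablet molybdenum intake from the assayed total molybdenum content of the dispensed batch or batches, and report the nominal-content result beside it. The figure could come from ICP-MS on a few tablets, or from a release assay that can be converted to total molybdenum. An assay of the active ingredient alone may not be enough, because tetrathiomolybdate hydrolyses to molybdate (Protocol 4.2) and the balance counts both.

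If nominal content stays as the main analysis, add a sensitivity analysis of molybdenum balance over the batch content range. In that case also reconcile SAP 4.1 and 7.2.2 with Protocol 8.1.1, so that the documents agree on whether drug intake is assayed or calculated. SAP 7.4.3 may keep the nominal dose with a sentence stating the caveat.

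The cost is obtaining a batch figure, linking kit batch numbers to participants, and some SAP wording. Protocol Table 6 already puts the batch number on the kit label. No participant procedure changes. The documents do not show whether a suitable release assay exists; if none does, a small tablet assay is the added work.

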7.2.3. Exploratory Analyses

The exploratory endpoint analyses will be conducted on the FA Set. The exploratory endpoints will be analyzed in the same manner as the primary endpoint. Additionally, plasma copper:molybdenum ratio, copper:molybdenum ratio in urine and feces, and ratio of cumulative Cu and Mo Inputs and Outputs will be examined. The ratios will be derived at the patient level daily and then summarized. The periods of interest described in Section 7.2 will be utilized as appropriate.

Descriptive statistics for treatment period 1 (15 mg) and treatment period 2 (30 mg) for the net copper balance will be presented to understand the dose response relationship. A boxplot with jitter scatterplot will be included to show the net copper balance in the two dose groups.

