4.2. Scientific Rationale for Study Design

The study is designed as an open-label exploratory study to provide a descriptive assessment of copper balance in participants with WD, the target population for ALXN1840 therapy. The study is being conducted as a repeat-dose study to assess the effect of duration of ALXN1840 treatment and the effects of intra-patient dose increase on copper and molybdenum balance in participants with WD. The intra-patient dose escalation schedule is similar to that employed in the current Phase 3 Study WTX101-301. The similar schedule was chosen to characterize the decoppering effects expected early with treatment. This study is designed to supplement the mechanism of action study in healthy participants (Study ALXN1840-HV-108). While healthy participants are expected to be adequate to assess the mechanism of action of ALXN1840, characterization of copper balance in the WD population will help to understand if there are differences in the magnitude of effect between the 2 populations as this may be important to understand the doses that may support a net neutral versus a net negative copper balance. Limited nonclinical data on copper elimination with tetrathiomolybdate suggested copper excretion may be at least maintained or increased with repeated dosing (refer to the current IB).

Therefore, the duration of the study and multiple collection periods will better characterize the pattern of copper elimination over time. Such information may be helpful in understanding the decoppering and maintenance phases.

As the study involves intensive diet control and sampling, the study is planned to be conducted in a small number of participants with WD who will be admitted to a CRU for 2 inpatient periods. Inpatient Period 1 includes a baseline and initial 15 mg/day collection period during the accumulation phase followed by an Outpatient Period; Inpatient Period 2 with a second collection period to support analysis of copper balance at 15 mg/day steady state and a 30 mg/day accumulation and steady state.

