6.3. Measures to Minimize Bias: Randomization and Blinding

Blinding and randomization are not applicable. This is an open-label study in which all participants are expected to receive ALXN1840.

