4. DESCRIPTION OF THE PROTOCOL

[figure not shown]
Study ALXN1840-WD-204 will be conducted as an open-label, repeat-dose study to evaluate the effects of ALXN1840 on copper balance in participants with Wilson Disease (WD).

Treatment-experienced (which includes standard of care therapies or ALXN1840) and treatment-naïve participants are eligible for this study. Eligible patients will be classified into one of two cohorts:

- Cohort 1 (treatment experienced): Patients who have received WD therapy for > 28 days
- Cohort 2 (treatment naïve): Patients who have received WD therapy for ≤ 28 days

Following Screening and enrollment, participants will check-in to the clinical research unit (CRU) on Day -8 for the Run-in Period. The purpose of the Run-in Period is to support diet equilibration (Day -7 through Day -5) and measure pretreatment copper and molybdenum balance (Day -4 through Day -1). Participants will remain on a copper/molybdenum-controlled diet throughout both the Inpatient Period 1 (Day -8 to Day 9) and Inpatient Period 2 (Day 23 to Day 40). The study design schematic is presented in Figure 1. While not in the CRU, participants will be encouraged to adhere to their usual copper-controlled diet.

Figure 1: Study Design Schematic

1. Participants eligible for the study will be enrolled on Day -7 and initiated on a copper- and molybdenum-controlled diet, which will be continued during Treatment Period 1 and Treatment Period 2 when in the CRU, through Day 39.
2. Participants will be admitted to the CRU for Treatment Period 1 on Day -8 and may be discharged on Day 9 or remain in the CRU for their own safety or to maintain the integrity of the conduct of the study. Participants who are discharged will be re-admitted on Day 22 or Day 23 for Treatment Period 2 and will remain in house until Day 40. To ensure flexibility, the Outpatient Period may be extended up to an additional 14 days with Investigator approval. In this situation, participants will be given additional study drug to support daily dosing throughout the Outpatient Period. In such cases, the actual Outpatient Period duration will be recorded and the participant will continue Inpatient Period 2 at Day 23.
3. Participants will be administered ALXN1840 at a dose of 15 mg/day on Day 1 through Day 28 and then increase to 30 mg/day on Day 29 through Day 39.
4. Participants will have 3 intake and output collection periods including:
 - Baseline Day -4 through Day -1

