5.1.3. Exploratory Objectives and Endpoints

The exploratory objectives and endpoints are:

Objectives	Endpoints
Determine dose response of ALXN1840 15 mg/day and 30 mg/day for copper balance in participants with WD	Assess dose response of ALXN1840 on copper balance focusing on copper balance
Determine the effect of treatment duration on copper balance in participants with WD	Determine the effect of time following initiation of ALXN1840 treatment on copper balance
Assess the effects of ALXN1840 on ceruloplasmin (Cp), ceruloplasmin-bound copper (CpC), LBC profiles in plasma in participants with WD	Cp, CpC, LBC, and Change in Cp at Days 1, 8, 25, 29, 36, and Day 39 compared with pre-dose
Assess dose proportionality at steady state of doses of ALXN1840 15 mg/day and 30 mg/day in participants with WD	Based on PK parameters

Objectives	Endpoints
Assess effects of ALXN1840 on copper:molybdenum ratio in plasma at steady state in participants with WD	Measure plasma copper:molybdenum ratios at steady state compared with pre-dose
Assess the effects of repeat-dose ALXN1840 on copper:molybdenum ratio in urine and feces in participants with WD	Mean daily copper:molybdenum ratio in urine and feces at steady state compared with pre-dose Baseline

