7.2.1. Primary Analysis

Based on the ALXN1840 mechanism of action, the primary objective of this study is to demonstrate a net negative copper balance with daily repeat-dose ALXN1840 treatment (15 mg and 30 mg) in participants with WD.

The primary analysis will be performed using the FA Set. Average daily copper balance and molybdenum balance will be calculated over the following periods:

- Day -4 through Day -1 representing pre-dose Baseline
- Days 1 through 8 representing the ALXN1840 15 mg/day accumulation period
- Days 25 through 28 representing the ALXN1840 15 mg/day steady-state period
- Days 31 through 35 representing the ALXN1840 30 mg/day accumulation period
- Days 36 through 39 representing the ALXN1840 30 mg/day steady-state period

Copper balance is defined by the difference in copper input and copper output. A negative Copper balance will indicate greater copper output than copper intake. Copper input is defined as the sum of all copper input as measured in all food and fluids over the specified period. Copper output is defined as the sum of all copper output as measured in urine and feces over the specified collection period. Many of the copper inputs and outputs will be collected with technical replicates and the mean of the replicates will be utilized in the analysis. The average daily copper balance is calculated as the difference in copper input and copper output during the specified period, divided by the total number of days in that period.

As ALXN1840 is expected to increase copper excretion through fecal excretion, copper in stool will be critical for determining copper balance. Because the timing of bowel movements can be irregular, assessment of copper and molybdenum balance will only include data up to the day of

the final bowel movement. For example, if the participant does not have a bowel movement on Day 8, then average daily copper balance for the Day 1 through Day 8 period will only include data from Day 1 through Day 7.

In the case of the 15 mg/day steady-state period (ie, Day 25 through Day 28), stool data collected on Days 29 - 30 samples may be used if needed to support assessments for the 15 mg/day dose. Use of these stool data (as needed) are consistent with an approximately 2-day gastrointestinal transit time.

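### The planned 15 mg versus 30 mg summary of copper balance mixes dose with time on drug and should be replaced by a paired steady-state contrast with an honest label

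*SAP*

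**What the plan says.** SAP section 4 gives one dosing order for all participants: "15 mg/day on Day 1 through Day 28 and then increase to 30 mg/day on Day 29 through Day 39". Protocol 6.3 states "Blinding and randomization are not applicable", and no group stays on 15 mg by design.

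SAP 7.2.1 defines two balance windows per dose. For 15 mg they are "Days 1 through 8 representing the ALXN1840 15 mg/day accumulation period" and "Days 25 through 28 representing the ALXN1840 15 mg/day steady-state period". For 30 mg they are Days 31-35 (accumulation) and Days 36-39 (steady state).

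For dose response, SAP 7.2.3 plans "Descriptive statistics for treatment period 1 (15 mg) and treatment period 2 (30 mg) for the net copper balance", which "will be presented to understand the dose response relationship", plus a boxplot by dose group. It does not say which windows make up each period. There is no time term, pairing or caveat, and SAP 9.3 adds no further methods.

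Treatment duration has its own exploratory endpoint in SAP 5.1.3: "Determine the effect of time following initiation of ALXN1840 treatment on copper balance". Protocol 4.2 adds that limited nonclinical data "suggested copper excretion may be at least maintained or increased with repeated dosing".

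**The concern.** The two dose groups are the same people at two stages of treatment. Any change in copper balance that comes from being on drug longer appears in the 30 mg minus 15 mg comparison and would be read as dose response. The plan treats duration as an open question, yet nothing in the dose-response summary separates the two. The early 15 mg window makes this worse, because the SAP itself classes it as a period in which drug is still accumulating.

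The study is meant to help distinguish a decoppering dose from a maintenance dose, and this SAP supports regulatory submissions. A rise in excretion with time would be credited to 30 mg. A waning effect would hide a real benefit of 30 mg. Protocol 4.2 gives grounds for either: excretion held or rising with repeated dosing, and decoppering effects anticipated early in treatment.

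**Working it through.** The documents give no SD, effect size or power for this comparison, so there is no planned figure to reproduce. The check asks how far apart in time the two doses lie, and what the contrast shows when dose has no effect.

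**1. Separation in time (SAP 7.2.1 windows)**

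- 15 mg: 8 days with mean Day 4.5 and 4 days with mean Day 26.5. Pooled mean = (8 × 4.5 + 4 × 26.5)/12 = Day 11.8.
- 30 mg: 5 days with mean Day 33 and 4 days with mean Day 37.5. Pooled mean = (5 × 33 + 4 × 37.5)/9 = Day 35.0.
- Pooled gap: 23.2 days. Steady-state gap: 37.5 − 26.5 = 11 days.
- In none of the 12 × 9 = 108 pairs does a 30 mg day come before or on a 15 mg day. The correlation of dose with day is 0.81.
- With the full 14-day outpatient extension, the later windows move by 14 days. The pooled gap becomes 49.0 − 16.5 = 32.5 days; the steady-state gap stays at 11.

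Pooling by day is my reading of treatment period 1 and 2, since SAP 7.2.3 does not define them.

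**2. Accumulation only, no dose effect**

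Inputs: total molybdenum half-life of 24 to 51 h (Protocol 2.2) and bowel transit of about 40 h (Protocol 4.1), with 0 h as the other extreme. Assume the effect on balance builds up as 1 − exp(−k(t − lag)), with k = ln 2/half-life, to the same full effect at both doses. Let A be the mean fraction of full effect over Days 1-8 (192 h):

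A = [(192 − lag) − (1 − exp(−k(192 − lag)))/k]/192

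The later windows are at essentially full effect, so the pooled contrast is about (8/12) × (1 − A).

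| Half-life | Transit | A | Pooled contrast | Days 36-39 minus 25-28 |
|---|---|---|---|---|
| 24 h | 0 h | 0.820 | 12% | <0.1% |
| 24 h | 40 h | 0.614 | 26% | <0.1% |
| 51 h | 0 h | 0.645 | 24% | <0.1% |
| 51 h | 40 h | 0.457 | 36% | <0.1% |

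Percentages are of the full drug effect, in the direction of 30 mg looking stronger. If the two windows per dose are averaged with equal weight, the contrast is (1 − A)/2, or 9% to 27%.

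**3. A slower duration effect, no dose effect**

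The shapes are assumed, and the effect is scaled to 100% at Day 39.

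- Linear: pooled contrast 23.2/39 = 59%; steady-state contrast 11/39 = 28%.
- Saturating, 1 − exp(−t/τ) with τ from 5 to 40 days: pooled 30% to 56%; steady-state 0.5% to 20%.

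**4. Would subtracting the 15 mg slope help?**

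The 15 mg windows are 26.5 − 4.5 = 22 days apart, so the correction for 11 days is 11/22 = 0.5 of their difference. Under the model in step 2 this removes 0.5 × (1 − A), or 9% to 27% of the full effect, that was never there, and makes 30 mg look worse than it is. Under the saturating curves it over-corrects by 10% to 25%. With equal, independent period variances the SD rises by √((1 + 1.5² + 0.5²)/2) = √(3.5/2) = 1.32.

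**The case against.** The study is exploratory and descriptive. Protocol 9.1.1 and SAP 7.2.1.4 rule out formal testing, and within-patient escalation was a deliberate choice. SAP 7.2.1 already reports all four treatment windows separately and plots daily balance, so a careful reader can see the change within 15 mg. No analysis can fully separate dose from duration in this design. All of that is true, and it limits the point to interpretation. It does not justify a summary that SAP 7.2.3 itself labels as dose response, when a less distorted contrast is available from the same data.

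Three stronger readings are tempting, and the documents do not support them:

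- *The plan expects excretion to rise with time.* Protocol 4.2 is conditional, rests on limited nonclinical data, and includes excretion merely being maintained, which means no trend.
- *The comparison has an inflated false-positive rate.* No test, confidence interval or decision rule is planned for copper balance, so there is no error rate to inflate.
- *The 15 mg data give a dose-free duration slope that can be subtracted, with dose response declared only if the adjusted interval excludes zero.* The early window is still accumulating drug, so the correction is itself biased (step 4), and such a rule would add inference to a descriptive study.

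**Conclusion.** The point holds as a matter of interpretation. On the planned schedule, the 15 mg versus 30 mg summary in SAP 7.2.3 cannot be read as dose response. Pooled over the SAP 7.2.1 windows, it shows a spurious 30 mg gain of about 12-36% of the full drug effect from accumulation alone. The paired steady-state contrast is essentially free of that part, but a slower duration effect could still enter it: 28% of the Day-39 effect if linear, 0.5-20% if saturating.

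The 12-36% rests on day-weighted pooling, on the effect following plasma accumulation, and on the protocol's half-lives and transit time. The duration figures rest on assumed shapes. The sign is not fixed: a waning effect would mask a dose effect. The strict ordering describes the schedule, not every individual, because Protocol 4.1 (Table 4) and 6.6 allow participants to stay on 15 mg or have the dose reduced.

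**What to change.** In SAP 7.2.3:

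1. Define the dose contrast as the within-participant difference in mean daily copper balance, Days 36-39 minus Days 25-28, in participants who took 30 mg. Show it as paired data (individual lines and differences) instead of a boxplot of two dose groups.
2. Label it *effect of the dose increase plus about 11 further days of treatment*, and state that dose and duration cannot be separated without an assumed time trend.
3. Beside it, show the 15 mg change from Days 1-8 to Days 25-28 for context, noting that it includes drug accumulation. Give actual days on drug where the Outpatient Period was extended.
4. Name the windows used, so that the period labels are unambiguous. The study schematic starts Treatment Period 2 at re-admission on Day 22 or 23. If that definition were applied here, 4 of the 13 scheduled window days (Days 25-28) would be at 15 mg, in a period that SAP 7.2.3 labels 30 mg.

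I would not add a slope-adjusted contrast or a confidence-interval rule for declaring dose response.

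Cost: SAP wording, one derived difference and a changed figure, with no new data. The dose summary no longer uses Days 1-8 and 31-35, which remain in the primary tables, and the stated conclusion is more modest.
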